### **5.2.2. Preoperative evaluation**

All the patients include in the ERAS protocol will undergo a preoperative multidisciplinary evaluation performed by the ERAS team. During this evaluation, all information regarding all the step of the ERAS protocol will be given to the patients and all the information regarding the preoperative step to follow, such as smoking quit or alcohol use. Moreover, information about the entire postoperative ERAS step that the patients needed to follow during the hospitalization will be given. Education and discharge plan will be discussed.

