#### **5.3. Data collection and analysis**

A baseline survey will be conducted to assess the awareness and knowledge of health care professional in charge of perioperative care. From November 2021, we will put in place an ERAS protocol for laparoscopic cholecystectomies. Patients living in Kigali and near Kigali having an easy communication means will be sensitized to adhere to the program.

A multidisciplinary team (Surgeons, Anesthesiologists, nurses, anesthetists and psychologists) will be mobilized to participate in the team. A google sheet questionnaire will be designed to collect information about the awareness and knowledge of perioperative health care professional about ERAS programme and then

a modified ERAS protocol will be put in place and data collection will be done using a coded checklist form and consecutive selection of patients will be done during the study period until we reach at least 50 patients. The operative procedures and instrumentation will be standardized for laparoscopic cholecystectomy, and surgeons who will perform the procedures will be having expertise in laparoscopic cholecystectomy. Reasons for conversion from laparoscopic to open cholecystectomy will be recorded and documented. Emergency patients and patients defined as ASA IV and pediatric patients aged below 16 years will be excluded.

Data will be collected for age, gender, indications for surgery, American Society of Anesthesiology (ASA) class, operative time, adverse events (pain, nausea and vomiting), length of hospitalization, and intra- and post-operative complications. The expenses of surgery and in-hospital care will be calculated and analyzed. On discharge, on day 3 of discharge, day 10, day 15 and day 30 of discharge patient will report outcomes and will be recorded by Surgical Recovery Scale. After discharge, the patients will be called or texted on phone to know about their status and collect information. Data will be recorded using EXCEL. Statistical analysis will be done using SPSS software and the one-way analysis of variance (ANOVA) test, the Chi-square test, and the t Student's test will be used when appropriate for comparisons.

A Univariate analysis will be done to determine variables associated with the length of hospital stay. Pearson's chi square will be calculated to compare variables and..

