## **6. Expected Results**

Table 1: Level of awareness and knowledge of ERAS among perioperative care health professionals

Table 2: Baseline characteristics of patients

Table 2: Acceptance rate of patients in ERP

Table 3: Rate of adverse events (Stress, fatigue, pain, nausea and Vomiting)

Table 4: Complications of laparoscopic cholecystectomy

Table 5: The average length of hospital stay

Tableau 6: Cost of laparoscopic cholecystectomy

Table 7: Rate of overnight and readmission

Table 8: Overall satisfaction of patients after laparoscopic cholecystectomy in ERP

Table 9: Comparative analysis of length and independents variables

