## **12. Conclusion**

The minimally invasive surgical procedures proceed towards patient safety without increased fatal complications

The quality of recovery and patient satisfaction are among clinical outcomes should interest the surgeons as indicator of quality of care to patients.

Laparoscopic cholecystectomy combined with ERAS can effectively treat a variety of benign, non-acute gallbladder diseases with shortened waiting time and postoperative hospital stay. ERAS benefits the hospital with a rapid bed turnover rate, and reduces cost for surgery and hospitalization

My study will determine if the ERP is feasible in our context and proposes recommendations in order to improve the quality of recovery of surgical patients and improve the bed turnover in different referral hospitals in Rwanda using enhanced recovery protocols.

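### The Surgical Recovery Scale has no pre-operative score, so it can show level and change since discharge but not return to the patient's own starting state

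*Protocol*

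**What the plan says.** Section 5.3 of the protocol fixes the times, "On discharge, on day 3 of discharge, day 10, day 15 and day 30 of discharge patient will report outcomes", and in the same sentence the instrument: "patient will report outcomes and will be recorded by Surgical Recovery Scale". Patients are taken consecutively under the ERAS protocol until at least 50 are reached, and no concurrent group is described.

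Other places where a pre-operative score might have been planned do not contain one:

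- The only survey that Section 5.3 calls a baseline is of staff: "A baseline survey will be conducted to assess the awareness and knowledge of health care professional in charge of perioperative care".
- The list of patient data in Section 5.3 begins "Data will be collected for age, gender, indications for surgery, American Society of Anesthesiology (ASA) class, operative time, adverse events (pain, nausea and vomiting" and goes on to length of stay and complications. It names no pre-operative recovery, stress or fatigue score.
- Section 5.2.2 says that ERAS patients "will undergo a preoperative multidisciplinary evaluation performed by the ERAS team". Its stated content is information, education and discharge planning.
- Section 6 announces "Table 2: Baseline characteristics of patients" by title only.

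Stress and fatigue appear in specific objective 2 (Section 4.2) and in the adverse-event table planned in Section 6. Section 12 remarks: "The quality of recovery and patient satisfaction are among clinical outcomes should interest the surgeons as indicator of quality of care to patients".

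**The concern.** Recovery is a change relative to something. With no concurrent group, the natural reference is each patient's own state before the operation, and the schedule does not record it. A middling score on day 30 could mean slow recovery from surgery. It could equally mean that the patient has returned to a state already limited by gallbladder symptoms or other illness. The two readings say different things about the programme.

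The same ambiguity affects stress and fatigue. Both can be present before an elective operation. If they are counted only afterwards, the reported frequency mixes what the patient brought to hospital with what followed surgery.

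This cannot be left to the statistical analysis plan. The protocol sets the collection times, and a missing pre-operative score cannot be created once the patient has had the operation.

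**Working it through.** There is no stated figure to reproduce. The check is of which quantities the schedule allows.

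**1. Count of assessments.** Section 5.3 gives discharge and days 3, 10, 15 and 30: five after surgery and none before.

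**2. What can be computed.** Let B be the pre-operative score, D the score at discharge and F(t) the score at a later time t.

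- Level: D and F(t) are observed.
- Change since discharge: F(t) − D is observed.
- Loss from surgery: D − B is not observed.
- Return to the starting state: F(t) − B = [F(t) − D] + [D − B]. The first bracket is observed and the second is not.

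So F(t) − B cannot be obtained at any of the five times, and the share of patients with F(t) back at B cannot be estimated.

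**3. Whether discharge can stand in for B.** Section 5.2.6 makes discharge depend on, among other things, absence of complications or symptoms, independent movement and pain control on oral drugs. D is therefore taken after a recovery threshold has been passed. Its timing also varies. Section 5.2.5 places discharge from 24 hours after surgery, while Section 2 describes two to three days after surgery under current practice. A change measured from D misses the initial loss and much of the early recovery.

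**4. Stress and fatigue.** Setting Sections 4.2, 5.3 and 6 side by side, the two are to be reported as post-operative events, and no pre-operative value is listed for either. A complaint seen after surgery may be new, worsened or unchanged, and the planned data do not separate the three.

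**5. Whether a baseline would also add precision.** Assume a correlation r of 0.5 to 0.7 between pre-operative and later scores. The documents give no value.

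- Adjusting for baseline in a regression or a group comparison removes r² of the variance: 0.25 to 0.49. The corresponding factor 1/(1 − r²) is 1.33 to 1.96.
- This study has one cohort. Adjusting for that cohort's own baseline does not sharpen its mean follow-up score.
- For a simple change score with equal standard deviations, the variance relative to the raw score is 2(1 − r): 1.0 at r = 0.5 (no gain) and 0.6 at r = 0.7.

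The case for a baseline therefore rests on interpretation, not on sample size.

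**The case against.** **The protocol does not promise this.** The aim at the end of Section 2, the general objective (4.1) and the six specific objectives (4.2) do not name quality of recovery or return to the pre-operative level. Section 12 makes only a general remark, and the opening page attaches better recovery to the wider laparoscopic programme. Sections 5.3 and 6 list no analysis or table of the scale. All of this stands. A reader might infer that the study fails one of its stated objectives, and the documents do not support that. What remains is that the protocol collects the scale five times per patient on a schedule that leaves the scores hard to interpret.

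**The link to fatigue events is indirect.** Nothing says that stress or fatigue events are derived from the scale, or how such an event is defined. The adverse events listed in Section 5.3 are pain, nausea and vomiting. A reader might infer that the planned fatigue rate is shown to be inflated, and it is not. The supported statement is narrower: with no prior value planned, existing and new complaints cannot be separated.

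**The absence may be incomplete reporting.** The coded checklist is not shown, and the data list is not exhaustive, since body mass index enters the regression but is not listed. This lowers certainty a little. The scale's own times are nevertheless stated explicitly, and all fall at or after discharge.

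**The instrument is not described.** Its items and recall period are not given, so how far its scores mix usual state with surgical effect cannot be judged from the documents. This also stands, and it is a reason to check that the items can be answered before surgery.

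**Conclusion.** The point holds as a limit on interpretation. With five scores after surgery, none before and no concurrent group, the study can report level and change since discharge. It cannot report loss from, or return to, the patient's own pre-operative state, and it cannot separate existing from new stress and fatigue. No later analysis can repair this.

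Its weight is modest. It concerns a secondary outcome for which no analysis is listed, and it leaves length of stay untouched. A reader might also infer that a baseline is worth 1.3 to 2 times the patients. That does not follow for a single-cohort mean or for a simple change score, and the correlations behind it are assumed.

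The conclusion rests on one assumption: that the unseen checklist holds no pre-operative recovery, stress or fatigue score. It is best treated as a cheap improvement.

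**What to change.** In Section 5.3, add one administration of the Surgical Recovery Scale, with stress and fatigue items, at the pre-operative evaluation of Section 5.2.2. Before enrolment, confirm that the items make sense to a patient who has not yet had surgery.

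Then:

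- report, at each of the five times, the score itself, the change from the pre-operative value and the share of patients back to it, with the definition of being back fixed in advance;
- report stress and fatigue as new or worsened relative to the pre-operative value.

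Keep the absolute scores in the report, because a symptomatic patient can be back at a poor starting level.

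The cost is six administrations per patient instead of five, a few minutes each for at least 50 patients, at an evaluation that is already planned and where consent is also taken (Section 8.3). It adds no visit and changes no treatment or discharge rule. It must be in place before the first operation under the programme.

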### **5.2.3. Anaesthesiologic protocol**

No premedication will be administered. Two different types of anesthesiology technique will be used: general anesthesia with local infiltration of the surgical incision. In all cases restricted intraoperative fluid administration (6–8 ml/kg/h) and prevention of hypothermia during surgery will be used. Moreover, no opioids will be used during all the perioperative period. Antibiotic prophylaxis will be given in agreement with the hospital protocol. Analgesia and Prevention of PONV will be given. Immediate postoperative monitoring will be performed in the recovery room where the pain numeric rating scale (NRS) will be routinely evaluated by the anesthesiologist or the NPA.

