Continuous variables were presented as mean  $\pm$  standard deviation or median (range) when appropriate and categorical variables will be presented as frequency (percentage). A Univariate analysis will be performed through a stepwise linear regression model using length of hospital stay as dependent variable and age, BMI, gender, ASA score, intraoperative infusions, pain, analgesia, nausea, vomiting, 30 days-readmission rates, presence of complications and mortality as independent factors. Variables with significant link will be crossed with outcome variables to draw their correlation overnight, using Multivariate logistic regression A p value  $< 0.05$  will be considered statistically significant.

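### The length-of-stay model includes intraoperative infusions but not operative time, so if infusion is entered as a volume, an effect of long operations could be read as a fluid effect

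*Protocol*

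**What the plan says.** Four statements in the protocol bear on this.

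- **Model** (section 5.3): "A Univariate analysis will be performed through a stepwise linear regression model using length of hospital stay as dependent variable".
- **Candidates** (section 5.3): "age, BMI, gender, ASA score, intraoperative infusions, pain, analgesia, nausea, vomiting", then readmission within 30 days, complications and mortality. The list is closed at twelve. Intraoperative infusion is on it; operative time is not. Predictors that reach significance are then taken into a multivariable logistic regression.
- **Data collected** (section 5.3): "Data will be collected for age, gender, indications for surgery, American Society of Anesthesiology (ASA) class, operative time", followed by adverse events, stay and complications. Operative time is therefore available. Infused volume, weight and BMI are not on this list.
- **Fluid target** (Anaesthesiologic protocol, section 5.2.3): "In all cases restricted intraoperative fluid administration", given as 6–8 ml/kg/h.

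No section says whether the infusion variable is a total volume, a volume per kg or a rate.

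**The concern.** When the rate is held in a narrow band, the volume a patient receives is mainly decided by how long the operation lasts and how much the patient weighs. A model that offers volume but not duration lets volume stand in for duration. Stepwise selection cannot correct this, because operative time is never offered to it.

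Limited intraoperative fluid is one of the pathway elements in the table of section 5.2.1, and section 7 promises recommendations to hospitals in Rwanda. A result that reads as more fluid, longer stay could be taken as evidence for that element when it reflects only longer or harder operations. The variable needed to separate the two is already collected.

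**Working it through.** **The plan's own figures.** The protocol gives no figure for this analysis. Its one design number is 50–70 patients, for a proportion of 5%, margin ±5% and population 1600. The upper end reproduces: 1.96² × 0.05 × 0.95 / 0.05² = 72.99, and 72.99 / (1 + 71.99/1600) = 69.8. It serves here only as the sample size.

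**Inputs from the protocol.** Rate 6–8 ml/kg/h; n = 50 and 70; significance level 0.05 (two-sided assumed).

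**Assumptions not in the protocol.** Rate uniform on 6–8; operative-time coefficient of variation (CV) 25–50%; weight CV 15–25%; the three independent; operative time taken as the infusion period.

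**Step 1: what a volume measures.** Volume = rate × weight × time, so the log-variances add, each being ln(1 + CV²).

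- Rate: SD = √(2²/12) = 0.577, CV = 0.577/7 = 8.2%, log-variance 0.0068.
- Time at CV 40%: ln(1.16) = 0.1484.
- Weight at CV 20%: ln(1.04) = 0.0392.
- Sum 0.1944. Shares: time 76%, weight 20%, rate 3.5%.

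Over the assumed ranges, time carries 47–88% and rate 2–8%. For volume per kg, weight drops out: at time CV 40% the share of time is 0.1484 / (0.1484 + 0.0068) = 96%.

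**Step 2: effect of having BMI in the model.** BMI is already a candidate and removes much of the weight component. In a simulation with time CV 20–50% and BMI CV 15–20%, the correlation of volume with operative time was 0.63–0.91 unadjusted and 0.82–0.95 after adjusting for BMI. Adjusting for BMI therefore makes volume a purer stand-in for time.

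**Step 3: how often a false fluid effect appears.** Stay was simulated to depend on operative time only, with no fluid effect (2000 studies per setting, time CV 30% and 40%). Stay was regressed on BMI and volume. Share of studies with volume significant:

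| n | correlation 0 | 0.3 | 0.4 | 0.5 |
|---|---|---|---|---|
| 50 | 5% | 48–51% | 74–79% | 91–94% |
| 70 | 4–5% | 63–72% | 87–90% | 98–99% |

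With volume alone, without BMI, the figures for correlations 0.3–0.5 were 45–91% (n = 50) and 61–98% (n = 70).

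Hand check at n = 50, correlation 0.4, time CV 40%: expected partial correlation about 0.4 × 0.93 = 0.372. Fisher's z is 0.391 × √46 = 2.65, and Φ(2.65 − 1.96) is about 75%, near the simulated 79%.

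**Step 4: the alternatives.** With operative time added to the model, volume was significant in 4–5% of studies. With infusion entered as a rate and no operative time, the figure was 4–6%. Both are close to the nominal level.

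**The case against.** A reader might infer that the plan will credit fluids with the effect of long operations, or that it cannot show a fluid effect in any form. The document supports neither, for these reasons.

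- **The unit is undefined.** The protocol states intravenous fluid only per kg per hour. Entered as a rate, infusion is not a proxy for time. This stands, and makes the concern conditional on volume coding.
- **The band is a target.** This is a first implementation, and delivered rates may stray. With an assumed rate CV of 30%, weight CV of 20% and time CV of 25–40%, rate explains 31–46% of log volume: 0.0862/0.2738 at time CV 40% and 0.0862/0.1860 at 25%. A fluid signal could then exist, although time would still confound it.
- **The planned procedure was not simulated.** Twelve candidates enter stepwise, including complications, pain, nausea and vomiting. These may carry part of the effect of a difficult operation and compete with volume. The percentages in the table are not error rates of the plan.
- **The stay–time correlation is assumed.** Elective cases, standardised technique, experienced surgeons and criterion-based discharge could make it weaker.
- **Operative time is not shut out altogether.** Section 5.3 also plans a general univariate search for variables associated with stay, where it could appear. That would show its association but would not adjust the infusion coefficient for it.
- **Little rests on this model.** No objective concerns fluids or predictors of stay.

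These points limit the size and certainty of the problem. The omission remains: the candidate list names its variables and leaves out a collected confounder of one of them.

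**Conclusion.** The concern holds conditionally. If infusion is entered as a volume, total or per kg, and the fluid target is broadly followed, the variable mostly reflects operative time (and weight, if total). Any real link between duration and stay could then be reported as a fluid effect. If infusion is entered as a rate, the confounding is small, but the variable has little spread when the target is followed, so a fluid effect would be hard to detect.

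The size cannot be fixed from the document. It runs from about 5% false findings when stay is unrelated to operative time to roughly 45–98% for correlations of 0.3–0.5, in a simplified model rather than the planned stepwise one. The consequence is confined to the explanatory analysis in Table 9 and the logistic regression that follows it. Average stay, complication rates, acceptance and cost are untouched. The change is worth making because it is cheap.

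**What to change.** In section 5.3:

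1. Add operative time to the candidate predictors of stay. To keep the count at twelve, it could replace mortality, which is likely to have almost no events in 50–70 elective patients.
2. Define the infusion variable as the delivered rate in ml/kg/h, meaning what the patient received rather than the target.
3. Add infused volume and weight to the data list. Neither is there now, and weight is also needed for the planned BMI.

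The cost is one line in the analysis text and two checklist items. The downside is that the rate term may be imprecise if delivered rates stay close to the target, and the report should then say that the data cannot tell much about fluids. No element of fluid management changes.

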Laparoscopic surgery has helped to minimize surgical trauma in an increasing number of surgical procedures and avoids drains. The anesthetist makes preferential use of loco-regional techniques, avoids perioperative fluid overload, and prevents postoperative nausea and vomiting. After surgery, early feeding and mobilization are encouraged and facilitated by a multimodal analgesia strategy that spares opioids and limits their side effects.

ERPs reduce the incidence of medical complications by 50 %, including fewer infectious complications and a possible positive impact on survival after oncologic surgery. Hospital length of stay is shortened (2)[SEP] (12) (13) (14) (7) (10).

ERAS has been shown to have important clinical and economic benefits and significant reductions in length of hospital stay and the implementation of ERAS pathways improves clinical outcomes and induces substantial economic gains. ERAS is the current surgical revolution (15) (16).

Cholecystectomy is one of the commonest general surgical operations. Laparoscopic cholecystectomy is currently the most favored approach. As it is associated with less postoperative pain and ileus, it allows early discharge of patients from the hospital (17) (18). Studies from the West have reported that 'day case laparoscopic cholecystectomy' is feasible and safe with success rate of between 69-92 percent (18) (19).

In two randomized groups comparing ambulatory care and overnight stay, the average hospital stay was 3.1 for overnight stay versus 1.7 for ambulatory care (Dirksen) and the ambulatory treatment was less expensive (20) (17). However, careful patient selection is essential in ensuring a high success rate (18).

ERAS is not known in Rwanda and there is no report from any sub African country describing laparoscopic cholecystectomy in ERP. We will conduct a prospective study to assess the feasibility; safety, patients' acceptance, LOS and bed turnover of laparoscopic cholecystectomy in a tertiary care hospital in the ERP.

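### The fixed factor list for the length-of-stay regression omits conversion to open surgery, so if conversions occur a few converted patients could lend part of their longer stay to listed factors

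*Protocol*

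**What the plan says.** Protocol section 5.3 states: "A Univariate analysis will be performed through a stepwise linear regression model using length of hospital stay as dependent variable". It then names the candidates: "age, BMI, gender, ASA score, intraoperative infusions, pain, analgesia, nausea, vomiting, 30 days-readmission rates, presence of complications and mortality as independent factors". That is twelve factors, and conversion is not one of them. A p value below 0.05 "will be considered statistically significant". Factors that pass go on to a second model: "Variables with significant link will be crossed with outcome variables to draw their correlation overnight, using Multivariate logistic regression". Section 6 reserves a table for the result: "Table 9: Comparative analysis of length and independents variables".

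On conversion, section 5.3 says: "Reasons for conversion from laparoscopic to open cholecystectomy will be recorded and documented". Each converted patient can therefore be identified. Patients are taken consecutively, and the only exclusions are these: "Emergency patients and patients defined as ASA IV and pediatric patients aged below 16 years will be excluded". Nothing in the protocol says that converted patients are removed, analysed apart, adjusted for, or counted under complications.

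The Background says of the laparoscopic approach: "As it is associated with less postoperative pain and ileus, it allows early discharge of patients from the hospital".

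**The concern.** Conversion is decided in theatre, before the postoperative stay begins. The Background itself ties the laparoscopic approach to less pain and earlier discharge, so a converted patient can be expected to have more pain and a longer stay. Higher analgesic use, more intraoperative fluid and more complications after conversion are plausible too, though the protocol does not say so. A common cause of the outcome and of several candidates is then missing from a list that the protocol has written out, and a candidate can act as a stand-in for it.

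With 50 to 70 patients, two or three long stays carry much weight in a linear regression. Table 9 could then show a factor as linked to stay when the link comes mainly from those few operations. The two-step procedure would carry the factor into the logistic model.

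**Working it through.** **What the protocol supplies.** It gives 50 to 70 patients (section 5.1), at least 50 enrolled, twelve factors and the 0.05 threshold (section 5.3). The test is taken as two-sided. There is no figure on conversion to reproduce: the protocol states no conversion rate, added stay or SD of stay. These are assumptions below, shown as ranges.

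**1. How many conversions to expect.** The expected number is n × c, and the chance of none is (1 − c)^n.

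| Assumed rate c | Expected, n = 50 | Expected, n = 70 | No conversion, n = 50 |
|---|---|---|---|
| 2% | 1.0 | 1.4 | 0.98^50 = 36% |
| 5% | 2.5 | 3.5 | 0.95^50 = 8% |
| 10% | 5.0 | 7.0 | 0.90^50 = 0.5% |

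At 2% and n = 50, the chance of at most one is 0.98^50 + 50 × 0.02 × 0.98^49 = 0.364 + 0.372 = 74%.

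**2. Direction and size of the bias for one factor.** Let conversion add Δ hours to the stay and raise a factor by δ SD, and let the factor have no effect of its own. Regressing stay on the factor alone gives an expected slope of about

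Δ · δ · c(1 − c) / [1 + δ² · c(1 − c)] hours per SD.

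- c = 2%, Δ = 24, δ = 1: 24 × 0.0196 / 1.0196 = 0.46 h.
- c = 5%, Δ = 48, δ = 1: 48 × 0.0475 / 1.0475 = 2.2 h.
- c = 10%, Δ = 72, δ = 1.5: 72 × 1.5 × 0.09 / (1 + 2.25 × 0.09) = 9.72 / 1.2025 = 8.1 h.

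The slope is positive whenever Δ and δ are positive, and zero if either is zero.

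**3. False-positive rate for one such factor.** This was simulated with n = 50 and 70, right-skewed residual stay and a test at 0.05.

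| Assumptions | c = 2% | c = 5% | c = 10% |
|---|---|---|---|
| 24 h added, SD 20 h, 1 SD shift | about 6% | about 7% | 11-13% |
| 48-72 h added, SD 10 h, 1-1.5 SD shift | 10-25% | 21-57% | 38-86% |

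An intermediate case (24 h added, SD 10 h, 1 SD shift) gives 11-15% at 5% conversion. Adding a conversion term, or dropping converted patients, brings the rate back to 4-6% throughout.

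**4. Four factors fitted together.** Pain, analgesia and fluids are set 1 SD higher in converted patients, and complications occur in 25% of converted against 5% of other patients. Residual SD is 12 h and added stay is 24-48 h. None of the four has a true effect, and only runs with at least one conversion and one complication are counted.

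- Per factor, the false-positive rate is 5-9% in the mildest case (2%, 24 h) and 24-35% in the strongest (10%, 48 h).
- The chance that at least one of the four is falsely significant is 23-71% at n = 50 and 23-79% at n = 70. With conversion in the model it is 16-19%, about what four tests at 0.05 give: 1 − 0.95^4 = 18.5%.
- At 5% conversion, 48 h and n = 50, the spurious coefficients average 1.9 to 2.0 h per SD for pain, analgesia and fluids, and 7.4 h for complications. With conversion in the model they average about 0.
- If conversion is unrelated to the four factors, nothing is inflated (18-19%).

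Neither simulation runs the planned stepwise selection over all twelve factors.

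**The case against.** The strongest objection is that a factor with no effect on stay is the wrong null for several items on the list. Section 5.2.6 makes absence of complications or symptoms, eating without nausea or vomiting, and pain relief on oral analgesics conditions of discharge. A patient in pain or with a complication stays longer by rule, whatever the approach. If conversion raises pain and pain delays discharge, pain lies on the path and is not a false stand-in. This stands. The zero-effect calculation fits intraoperative infusions best, pain and analgesia only in part, and complications least.

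Conversion is also not cleanly upstream. Section 5.3 collects intraoperative complications, and one of these can itself cause conversion. A conversion term forced into the model could then remove part of a genuine complication effect, and with one to five expected conversions it would be poorly estimated. With exactly one, the term amounts to deleting that patient. This stands against making a forced term the main remedy.

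The size also depends on the inputs. The mild assumptions leave almost nothing at 2% conversion, and the setting is elective, without ASA IV patients and with experienced surgeons. Operative time and indication for surgery are collected and left off the list too, and a statistical analysis plan might define the analysis set. What remains is that the protocol itself wrote out the list, and the omitted variable is one whose link to pain and stay the protocol states.

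A reader might infer more: that Table 9 will credit pain, analgesia, fluids and complications with the longer stay of converted patients, and that advice to change analgesia or fluids would follow. The documents do not support this. They give no conversion rate or added stay, and with no conversions there is no bias. Section 7 plans recommendations to adopt ERAS and test it in other surgery, and does not mention analgesia or fluids.

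**Conclusion.** The point holds in conditional form. The omission is a fact of the text, and an upward bias follows if conversions occur and go with both a longer stay and higher values of a listed factor. The false-positive rate for a factor with no effect of its own runs from about 6% to about 86%, against about 5% when converted patients are set aside or adjusted for. That range rests wholly on assumed inputs: conversion 2-10%, added stay 24-72 h, residual SD 10-20 h and a factor 1-1.5 SD higher in converted patients. It should not be read as the error rate of the planned stepwise procedure.

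The weight is minor. Table 9 is exploratory, and the complications, average stay, cost and readmission results (Tables 4 to 7) do not depend on this model.

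**What to change.** In section 5.3 and Table 9, report the length-of-stay model twice: for all patients, and restricted to operations completed laparoscopically. State the number of conversions beside it. Treat as determinants of stay only those factors whose association persists in the restricted model, judged on the estimate and its confidence interval as well as the p value. For complications, an association that disappears on restriction should be described as not separable from conversion, since a complication may have led to the conversion. A yes/no conversion term may be added to the all-patient model if there are enough conversions to estimate it.

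The cost is one extra model run on data already recorded, and the loss of a few patients in the restricted run. No clinical procedure changes.
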